Clinical Trial Protocol

Document Number:		c09063095-08
EudraCT No.:	2017-005043-33	
BI Trial No.:	1381.1	
BI Investigational Product:	BI 754091 (ezabenlimab)	
Title:	An open-label, Phase I trial to determine the maximum-tolerated dose and investigate safety, pharmacokinetics, and efficacy of BI 754091 in patients with advanced solid tumours	
Lay Title:	A trial to find and investigate a safe dose of a new substance (BI 754091) for patients with solid tumours	
Clinical Phase:	Phase I	
Physician		
Trial Clinical Monitor:	Phone: [REDACTED] Fax: [REDACTED]	
Coordinating Investigator		
Status:	Final protocol (revised protocol [based on global amendment 7])	
Version and Date:	Version: 8.0	Date: 07 Mar 2023
Page 1 of 144		
Proprietary confidential information. © 2023 Boehringer Ingelheim International GmbH or one or more of its affiliated companies. All rights reserved. <small>THIS DOCUMENT MAY NOT - IN FULL OR IN PART - BE PASSED ON, REPRODUCED, PUBLISHED OR OTHERWISE USED WITHOUT PRIOR WRITTEN PERMISSION.</small>		

CLINICAL TRIAL PROTOCOL SYNOPSIS

Name of company:		Boehringer Ingelheim	
Name of finished product:		N.A.	
Name of active ingredient:		BI 754091	
Protocol date: 22 Sep 2016	Trial number: 1381.1		Revision date: 07 March 2023
Title of trial:	An open-label, Phase I trial to determine the maximum-tolerated dose and investigate safety, pharmacokinetics, and efficacy of BI 754091 in patients with advanced solid tumours		
Investigator			
Clinical phase:	I		
Objectives:	
Phase Ia Dose Escalation: To determine the maximum-tolerated dose (MTD) and the recommended Phase 2 dose (RP2D) and investigate the safety, pharmacokinetics (PK), biomarkers, and efficacy of BI 754091 in patients with advanced and/or metastatic solid tumours
 
Phase Ib Dose Expansion: To further evaluate the safety, the PK profile, biomarkers, and efficacy of the RP2D in 4 cohorts of patients with selected advanced and/or metastatic cancers
		
Methodology:	
Phase Ia Dose Escalation: Open-label, single arm, dose escalation (consecutive cohorts of escalating doses of BI 754091), Bayesian Logistic Regression Model (BLRM) with overdose control
 
Phase Ib Dose Expansion: Open-label, 4 dose-expansion cohorts
		
No. of patients:	Approximately 145 patients, depending on dose-escalation results		
Total entered:	
Phase Ia Dose Escalation: approximately 15 patients
 
Phase Ib Dose Expansion at the RP2D: 4 cohorts of approximately 30-40 patients each
		
Each treatment:	All patients participating in any part of this trial will receive BI 754091.		

Name of company:	Boehringer Ingelheim	
Name of finished product:	N.A.	
Name of active ingredient:	BI 754091	
Protocol date: 22 Sep 2016	Trial number: 1381.1	Revision date: 07 March 2023
Diagnosis:	
Phase Ia Dose Escalation: Patients with a confirmed diagnosis of advanced, unresectable, and/or metastatic solid tumours.
 
Phase Ib Dose Expansion: advanced and/or metastatic cancers including tumours with specific histology/tumour types and/or specific genetic profiles as specified in the following cohorts :
 
- Cohort 4: solid tumours including non-small-cell lung cancer (NSCLC), bladder cancer, melanoma, gastric cancer, ovarian cancer, triple-negative breast cancer (TNBC), and renal-cell cancer (RCC)- Cohort 5: Tumours with high tumour-mutational burden (TMB), excluding those with high microsatellite instability (MSI-high)- Cohort 6: Refractory squamous cell cervical, anal, and skin tumours.- Cohort 7: Recurrent human papillomavirus (HPV)-positive, or HPV-negative (per local testing), vaginal or vulvar squamous cell carcinoma (VSCC), not amenable to surgery.	
Main criteria for inclusion:	
Phase Ia Dose Escalation – adult patients with a confirmed diagnosis of advanced, unresectable, and/or metastatic solid tumours (any type) who have received all therapy known to confer clinical benefit (including anti-PD-1 therapies, if relevant and if the last dose of the prior anti-PD-1 was received more than 60 days prior to starting study drug), or for whom no therapy of proven efficacy exists, or who are not amenable to standard therapies
 
Phase Ib Dose Expansion – adult patients with a confirmed diagnosis of select advanced, unresectable, and/or metastatic solid tumours who are anti-PD-1/PD-L1 naïve but have failed conventional treatment (excluding anti-PD-1/PD-L1 treatment), or for whom no therapy of proven efficacy exists, or who are not amenable to standard therapies.
 
All patients must have measurable lesions according to Response Evaluation Criteria in Solid Tumours (RECIST) v1.1 and/or Immune-Related Response Evaluation Criteria in Solid Tumours (iRECIST).
 
Additional specific criteria for the individual expansion cohorts include:
 
- Cohort 4: Advanced and/or metastatic solid tumours including NSCLC, bladder cancer, melanoma, gastric cancer, ovarian cancer, TNBC, and RCC- Cohort 5: Patients with tumours that are TMB-high: any tumour with TMB-high status (>10 mutations/Mb), excluding those that are MSI-high (TMB and MSI status based on any validated test)- Cohort 6: Patients with squamous cell cervical, anal, and skin tumours that are refractory to standard therapies.- Cohort 7: Patients with recurrent HPV-positive, or HPV-negative, vaginal or VSCC	

Name of company:	Boehringer Ingelheim	
Name of finished product:	N.A.	
Name of active ingredient:	BI 754091	
Protocol date: 22 Sep 2016	Trial number: 1381.1	Revision date: 07 March 2023
Test product:	BI 754091	
Dose:	Phase Ia Dose Escalation : starting dose is 80 mg (1 mg/kg for a 80-kg person) once every 3 weeks (q3w) Phase Ib Dose Expansion : the RP2D established in Phase Ia	
Mode of administration:	Intravenous infusion	
Duration of treatment:	BI 754091 will be given on Day 1 of 21-day cycles for up to 1 year, or until progressive disease (PD) or unacceptable toxicity in the absence of other withdrawal criteria. If the patient is benefiting clinically at 1 year, he/she may continue after a case by case review with the sponsor, but no longer than 31 August 2023.	
Endpoints	
Endpoints for the Phase Ia Dose Escalation:
 
Primary:
 
Number of patients experiencing dose-limiting toxicities (DLTs) graded according to the Common Terminology Criteria for Adverse Events (CTCAE Version 4.03/5.0), observed in the first cycle (3 weeks) in order to meet the objective of assessment of the MTD of BI 754091. 
Secondary:
 
The following PK parameters will be calculated: C_{max} and AUC_{0-504}, after single and multiple dose of BI 754091, as measured during the first and subsequent cycles (administration q3w) (if data permits)Number of patients experiencing DLTs from start of treatment until end of treatment (in all cycles)Confirmed Objective Response (OR) according to RECIST v1.1 assessed by the Investigator. 
Endpoints for the Phase Ib Dose Expansion:
 
Primary:
 
Number of patients with DLTs observed during the entire treatment periodConfirmed OR according to RECIST v1.1 as assessed by the Investigator 
Secondary:
 
Progression-free survival (PFS) according to RECIST 1.1 as assessed by the Investigator 
Safety will continue to be assessed by the recording of AEs, SAEs (including DLTs), physical examinations, laboratory evaluations, vital signs, and ECGs as:
 
Percentage of subjects with AEsPercentage of subject with SAEs	

Name of company:		Boehringer Ingelheim	
Name of finished product:		N.A.	
Name of active ingredient:		BI 754091	
Protocol date: 22 Sep 2016	Trial number: 1381.1		Revision date: 07 March 2023
Safety criteria:	
- Percentage of subjects with clinical relevant abnormalities in vital signs, laboratory evaluations or ECG parameters (note that clinically relevant abnormalities are those which have to be reported by the investigator as AEs). 
Adverse events (AEs) according to CTCAE v. 4.03 / 5.0, incidence of DLTs for determination of the MTD (Phase Ia dose escalation only), results of physical examinations, laboratory evaluations, vital signs, and electrocardiograms (ECGs).
		
Statistical methods:	
Phase Ia: Dose escalation is guided by a BLRM with overdose control that will be fitted to binary toxicity outcomes. The estimate of parameters will be updated as data are accumulated using the BLRM. At the end of dose escalation, the toxicity probability at each dose level will be calculated to determine an estimate of the MTD. If there are too few or no DLTs for BLRM guided dose selection, PK and/or biomarker data will be taken into consideration for RPIID determination.
 
Phase Ib: data collected during this phase will be recorded and presented in a descriptive fashion.
 
No hypothesis testing is planned in either phase.
		

Proprietary confidential information © 2023 Boehringer Ingelheim International GmbH or one or more of its affiliated companies

FLOW CHART 1: BI 1381.1 (REFMAL 473) PHASE IA (DOSE ESCALATION) TRIAL ASSESSMENTS

Flow Chart 1		Trial Treatment Days ^{a,b} Cycle = 21 Days							Post-Treatment Days ^b		
	Screening	Cycles 1, 2, and 4					Cycles 3, 5, and 6+	End-of-Treatment ^a (EOT) Visit	30-Day ^b Safety Follow-up	PFS Follow-up ^q	
Assessments	-28 to -1	1 (±2 C3+)	2 (±2 C3+)	4 (±2 C3+)	8 (±1 C1) (±2 C3+)	15 (±1 C1) (±2 C3+)	1 (±2)	(within 7 days of EOT)	(+2)		
Informed Consent ^c	X										
Inclusion/Exclusion Criteria	X										
Medical History and Demographics ^d	X										
Physical Examination ^{d, e}	X	X				X ^{e,m}	X	X	X	X	
ECOG Performance Status ^{d, e}	X	X					X (C3,5,7,9,etc)	X	X	X	
Vital Signs ^d	X	X	X	X	X	X	X	X	X	X	
12-Lead Digital Electrocardiogram ^{d, f}	X	X					X ^f	X	(X)		
Hematology and Clinical Chemistry Labs ^d	X	X			X ^m	X ^m	X		X		
Urinalysis ^d	X							X			
Pregnancy Test for Women of Child-Bearing Potential ^{d, g}	X	X					X	X		X	
Concomitant Medications	X	X	X	X	X	X	X	X	X	X	
Adverse Events	X	X	X	X	X	X	X	X	X	X	
Survival ^q										X ^q	
Blood Samples for Biomarkers [REDACTED] ^h		X	X		X		X	X			
Blood Samples for [REDACTED] ^{i, p}		X					X ^q	X	X		
Blood Samples for Pharmacokinetics ^{j, p}		X	X	X	X	X	X	X ^{j, p}	X ^j		
Biopsy ^k	(X)						(X) (end C2)	(X)			
Tumour Assessments ^{d, l}	X	Every 6 weeks (then every 9 weeks after 6 months of treatment)									
BI 754091 infusion		X					X				
DLT Assessment (report required at Phase Ia Cycle 1) ⁿ		X	X	X	X ^m	X ^m	X	X			

Flow Chart 1 Footnotes (Dose-Escalation)

- a All cycles are 3 weeks (21 days) in duration. Patients will continue treatment with BI 754091 until disease progression (PD) by RECIST and/or iRECIST, withdrawal of patient consent, an unacceptable toxicity occurs, or 1 year of treatment is completed, whichever occurs first. Patients will be allowed to stay on treatment in the case of initial radiological PD, if the Investigator feels that it is in the patient's best interest and the patient signs an informed consent describing this circumstance. In addition, patients without PD may stay on trial after 1 year on a case-by-case basis after discussion with the Medical Monitor and the sponsor but no longer than 31 August 2023. Day 1 of Cycle 1 is defined as the day when BI 754091 is first administered. During Phase Ia (dose escalation), Cycle 2 cannot begin without Safety Review Committee approval.
- b Days are calculated as calendar days.
- c Informed consent must be obtained \leq 28 days prior to the initiation of treatment.
- d Safety laboratory assessments including haematology, serum biochemistry, and urinalysis will be performed locally. The screening medical history and demographics, physical examination and Eastern Cooperative Oncology Group (ECOG) performance status, vital signs, electrocardiogram (ECG), haematology, clinical chemistry (sodium, potassium, phosphate, chloride, creatinine, calcium, venous bicarbonate HCO₃, albumin, total protein, AST, ALT, alkaline phosphatase, bilirubin, lactate dehydrogenase, serum glucose, c-peptide, serum cholesterol [baseline only], serum triglycerides [baseline only], serum creatinine, serum urea nitrogen [or urea], serum uric acid, and TSH, free T4, and free T3), urinalysis, and screening pregnancy test should be done \leq 14 days prior to initiation of treatment. Additionally, amylase and lipase should be analysed in case of symptoms of pancreatitis. If these assessments are performed within 72 hours of initiation of treatment, they do not need to be repeated on Cycle 1 Day 1 with the exception of the ECOG performance status, an abbreviated physical examination, vital signs (pre- and post-infusion), and a single ECG required prior to first trial dose. Tumour assessments (scans) should be performed \leq 28 days prior to initiation of treatment and copies may be collected by the sponsor or designee. Refer to Section 5.3 for additional details.
- e Physical examinations will be done at screening, on Day 1 of each treatment cycle, at the end-of-treatment (EOT) visit, and at the 30-day safety follow-up visit. However, patients will have an additional abbreviated physical examination (focused on the specific disease, at the Investigator's discretion) on Cycle 1 Day 15. ECOG performance status will be done at screening, on Day 1 of Cycles 1 and 2, on Day 1 of every other cycle beginning with Cycle 3, at the EOT visit, and at the 30-day follow-up visit.
- f Single digitalised ECGs must be done before blood work or other procedures after 5 minutes of rest at screening, Cycle 1 Day 1, Cycle 3 Day 1, Day 1 of every third cycle thereafter (Cycles 6, 9, 12, etc), at the EOT visit, and whenever the Investigator deems it necessary. An ECG is optional at the 30-day safety follow-up visit if the EOT visit ECG was normal and no drug-related abnormalities were detected in on-trial ECGs (see Section 5.3.3).
- g Women of child-bearing potential must have a serum β HCG pregnancy test at screening, on Day 1 of each cycle, and at the EOT visit. Beginning with Cycle 3, urine dipstick tests can be done on Day 1 of odd-numbered cycles (Cycles 3, 5, 7, etc).

Proprietary confidential information © 2023 Boehringer Ingelheim International GmbH or one or more of its affiliated companies

h [REDACTED] on Days 1 (pre-treatment), 2, and 8 of Cycles 1, 2, and 4, on Day 1 (pre-treatment) of Cycles 3, 5 through 12, 14, and 17, and at the 30-day follow-up visit. (see Section 5.5.2.1 and Appendix 10.4.1).

i Blood samples for [REDACTED] will be collected from all patients as presented in the tables in Appendix 10.4.1.

j Pharmacokinetic (PK) blood sampling: there is extensive PK sampling in Cycles 1, 2, and 4 and it is strongly recommended to follow the visit days and sampling time points as outlined in the Appendix 10.4.1 tables. The permitted visit windows should only be used if medically indicated.

k Patients in the dose-escalation cohorts may consent to optional paired biopsies:

- The equivalent of 2 fine needle biopsies (archival) from the most recent relapse (if within 6 months of trial start with no subsequent therapy); otherwise, a minimum of 2 fine needle biopsies must be freshly taken between screening and the day before first treatment with BI 754091.
- The equivalent of 2 fine needle biopsies on treatment at the end of Cycle 2 (6 weeks).
- Another biopsy (optional) should be taken upon PD (according to RECIST v1.1 and iRECIST), if possible. An optional biopsy should also be taken if a patient has stable disease over 3 subsequent disease assessment periods.

l Tumour assessments should be done according to RECIST v1.1 and iRECIST and should include CT/PET scans of the chest and abdomen and, if clinically indicated, imaging of any other known or suspected sites of disease (e.g., pelvis, brain) using an appropriate method (CT/PET scan or MRI). The same radiographic procedure must be used throughout the trial. In case of suspected (but not confirmed) bone metastasis at screening, tumour assessment at screening should include a bone scan. If bone lesions are already known or confirmed at screening, correlative imaging (X-ray or CT scan) should be performed. Correlative imaging should then be repeated at each tumour assessment (see Section 5.2.1 for more detail). Assessments will be performed by the Investigator at screening and every 2 cycles (6 weeks) for the first 6 months of treatment and once every 3 cycles (9 weeks) thereafter until PD or start of further treatment for disease, and at the discretion of the Investigator.

m Cycle 1 only

n Dose-limiting toxicities (DLTs) will be collected throughout the trial and will be assessed for dose-escalation decisions following Cycle 1. After a first cycle is completed, a BI DLT Assessment report must be sent to the Medical Monitor (see Section 4.1.5). Cycle 2 cannot begin without Safety Review Committee approval.

o If the decision is made to permanently discontinue BI 754091 during a scheduled visit, the EOT visit assessments should be performed instead of the scheduled visit assessments.

p [REDACTED] PK blood samplings are to be collected during Cycles 1 through 12, Cycle 14, Cycle 17, at the EOT visit, and the 30-day safety follow-up.

q Additional progression-free survival (PFS) follow-up visits after the 30-day safety follow-up visit will only be performed for patients who did not progress on treatment. These will be performed once every 12 weeks at least (by telephone) until PD, introduction of a new anti-cancer treatment, death, loss to follow-up, withdrawal of consent, or end of the whole trial.

Proprietary confidential information © 2023 Boehringer Ingelheim International GmbH or one or more of its affiliated companies

FLOW CHART 2: BI 1381.1 (REFMAL 473) PHASE IB (DOSE EXPANSION) TRIAL ASSESSMENTS

Flow Chart 2									Post-Treatment Days ^b		
	Screening	Cycles 1, 4, and 8				Cycles 2, 3, 5-7, & 9	Cycles 10, 11, 13, 14, 16, 17, etc	Cycles 12, 15, 18, etc	End-of-Treatment ^a (EOT) Visit	30-Day ^b Safety Follow-up	PFS, OS Follow-up ^{o,q}
Assessments	-28 to -1	1 (±2 C4+)	2 ^p (±2 C4+)	8 (±1 C1)	15 ^p (±1 C1) (±2 C4+)	1 (±2)	1 (±2)	1 (±2)	(within 7 days of	(+2)	
Informed Consent ^c	X										
Inclusion/Exclusion Criteria	X										
Medical History and Demographics ^d	X										
Physical Examination ^{d, e}	X	X				X	X		X	X	X
ECOG Performance Status ^{d, e}	X	X				X (C3,5,7,9)	X (C11, 13,17 etc)	X (C15, 21 etc)	X	X	X
Vital Signs ^d	X	X	X (C1)	X	X (C1)	X	X	X	X	X	X
12-Lead Digital Electrocardiogram ^{d, f}	X	X (C1)				X ^f		X	X	(X)	
Hematology and Clinical Chemistry	X	X				X		X			X
Urinalysis ^d	X								X		
Pregnancy Test for Women of Child-Bearing Potential ^{d, g}	X	X				X	X	X	X		X
Concomitant Medications	X	X	X (C1)	X	X (C1)	X	X	X	X	X	X
Adverse Events	X	X	X (C1)	X	X (C1)	X	X	X	X	X	X
Survival ^o											X ^o
Blood Samples for [REDACTED] ^h		X (C1)		X (C1)	X (C1)	X (C2)			X ^q		
[REDACTED]		X (C1)	X (C1)	X (C1)	X (C1)	X (C2)			X ^q		
Blood Samples [REDACTED]		X				X		X	X ^q	X ^q	
Blood Samples for Pharmacokinetics ^k		X		X		X		X	X ^{k,q}	X ^{k,q}	
Biopsy ^l	X					X (end C2)			(X) ^q		
Tumour Assessments ^{d, m}	X	Every 6 weeks (then every 9 weeks after 6 months of treatment)									

Trial Protocol

Proprietary confidential information © 2023 Boehringer Ingelheim International GmbH or one or more of its affiliated companies

Flow Chart 2									Post-Treatment Days ^b		
	Screening	Cycles 1, 4, and 8				Cycles 2, 3, 5-7, & 9	Cycles 10, 11, 13, 14, 16, 17, etc	Cycles 12, 15, 18, etc	End-of-Treatment ⁿ (EOT) Visit	30-Day ^b Safety Follow-up	PFS, OS Follow-up ^{o,q}
Assessments	-28 to -1	1 (± 2 C4+)	2 ^p (± 2 C4+)	8 (± 1 C1)	15 ^p (± 1 C1) (± 2 C4+)	1 (± 2)	1 (± 2)	1 (± 2)	(within 7 days of	(+2)	
BI 754091 infusion		X				X	X	X			

Flow Chart 2 Footnotes (Dose Expansion)

- a All cycles are 3 weeks (21 days) in duration. Patients will continue treatment with BI 754091 until disease progression (PD) by RECIST and/or iRECIST, withdrawal of patient consent, an unacceptable toxicity occurs, or 1 year of treatment is completed, whichever occurs first. Patients will be allowed to stay on treatment in the case of initial radiological PD, if the Investigator feels that it is in the patient's best interest and the patient signs an informed consent describing this circumstance. In addition, patients without PD may stay on trial after 1 year on a case-by-case basis after discussion with the Medical Monitor and the sponsor, but no longer than 31 August 2023. Day 1 of Cycle 1 is defined as the day when BI 754091 is first administered.
- b Days are calculated as calendar days.
- c Informed consent must be obtained ≤ 28 days prior to the initiation of treatment.
- d Safety laboratory assessments including haematology, serum biochemistry, and urinalysis will be performed locally. The screening medical history and demographics, physical examination and Eastern Cooperative Oncology Group (ECOG) performance status, vital signs, electrocardiogram (ECG), haematology, clinical chemistry (sodium, potassium, phosphate, chloride, creatinine, calcium, venous bicarbonate HCO₃, albumin, total protein, AST, ALT, alkaline phosphatase, bilirubin, lactate dehydrogenase, serum glucose, c-peptide, serum cholesterol [baseline only], serum triglycerides [baseline only], serum creatinine, serum urea nitrogen [or ureal], serum uric acid, and TSH, free T4, and free T3), urinalysis, and screening pregnancy test should be done ≤ 14 days prior to initiation of treatment. Additionally, amylase and lipase should be analysed in case of symptoms of pancreatitis. If these assessments are performed within 72 hours of initiation of treatment, they do not need to be repeated on Cycle 1 Day 1 with the exception of the ECOG performance status, an abbreviated physical examination, vital signs (pre- and post-infusion), and a single ECG required prior to first trial dose. Tumour assessments (scans) should be performed ≤ 28 days prior to initiation of treatment and copies may be collected by the sponsor or designee. Refer to Section 5.3 for additional details.
- e Physical examinations will be done at screening, on Day 1 of each treatment cycle, at the end-of-treatment (EOT) visit, and at the 30-day safety follow-up visit. ECOG performance status will be done at screening, on Day 1 of Cycles 1 and 2, on Day 1 of every other cycle beginning with Cycle 3, at the EOT visit, and at the 30-day follow-up visit.
- f Single digitalised ECGs must be done before blood work or other procedures after 5 minutes of rest at screening, Cycle 1 Day 1, Cycle 3 Day 1, Day 1 of every third cycle thereafter (Cycles 6, 9, 12, etc), at the EOT visit, and whenever the Investigator deems it necessary. An ECG is optional at the 30-day safety follow-up visit if the EOT visit ECG was normal and no drug-related abnormalities were detected in on-trial ECGs (see Section 5.3.3).

Proprietary confidential information © 2023 Boehringer Ingelheim International GmbH or one or more of its affiliated companies

- g Women of child-bearing potential must have a serum β HCG pregnancy test at screening, on Day 1 of each cycle, and at the EOT visit. Beginning with Cycle 3, urine dipstick tests can be done on Day 1 of odd-numbered cycles (Cycles 3, 5, 7, etc).
- h Blood samples for [REDACTED] for flow analysis will be collected (if feasible) during Cycle 1 on Day 1 (pre-treatment), Day 8, and Day 15, on Cycle 2 Day 1 (pre-treatment), and at EOT (see Section 5.5.2.1 and Table 10.4.2: 1).
- i Blood samples for cytokines will be collected (if feasible) during Cycle 1 on Day 1 (pre-treatment), Day 2, Day 8, and Day 15, on Cycle 2 Day 1 (pre-treatment), and at EOT (see Section 5.5.2.1 and Table 10.4.2: 1).
- j Blood samples for [REDACTED] will be collected from all patients as presented in Table 10.4.2: 1.
- k Pharmacokinetic (PK) blood sampling will be collected from all patients as presented in Table 10.4.2: 1.
- l The following fresh tumour biopsies will be mandatory for all patients in the Phase Ib dose-expansion cohorts of the trial (refer to Section 6.2.1.1):
 - 2 core needle biopsies or 1 punch biopsy (refer to lab manual for specifications) from the most recent relapse (if within 6 months of trial start with no subsequent therapy); otherwise, a minimum of 2 core needle biopsies or 1 punch biopsy must be taken between the start of screening and the day before first treatment with BI 754091.
 - 2 core needle biopsies or 1 punch biopsy on treatment at the end of Cycle 2 (6 weeks), preferably from the same lesion.
 - Another biopsy (optional) should be taken upon PD (according to RECIST v1.1 and iRECIST), if possible. An optional biopsy should also be taken if a patient has stable disease over 3 subsequent disease assessment periods.
- m Tumour assessments should be done according to RECIST v1.1 and iRECIST and should include CT/PET scans of the chest and abdomen and, if clinically indicated, imaging of any other known or suspected sites of disease (e.g., pelvis, brain) using an appropriate method (CT/PET scan or MRI). The same radiographic procedure must be used throughout the trial. In case of suspected (but not confirmed) bone metastasis at screening, tumour assessment at screening should include a bone scan. If bone lesions are already known or confirmed at screening, correlative imaging (X-ray or CT scan) should be performed. Correlative imaging should then be repeated at each tumour assessment (see Section 5.2.1 for more detail). Assessments will be performed by the Investigator at screening and every 2 cycles (6 weeks) for the first 6 months of treatment and once every 3 cycles (9 weeks) thereafter until PD or start of further treatment for disease, and at the discretion of the Investigator.
- n If the decision is made to permanently discontinue BI 754091 during a scheduled visit, the EOT visit assessments should be performed instead of the scheduled visit.
- o **Patients enrolled in Protocol Version 4.0 (expansion Cohort 4 and higher):** Additional overall survival (OS) and progression-free survival (PFS) follow-up visits after the 30-day safety follow-up visit will be performed once every 12 weeks at least (by telephone) until death, loss to follow-up, withdrawal of consent, or end of the whole trial. **Patients enrolled in Protocol Version 3.0 and earlier (expansion Cohort 1,2,3):** Additional PFS follow-up visits after the 30-day safety follow-up visit will only be performed for patients who did not progress on treatment. These will be performed once every 12 weeks at least (by telephone) until PD, introduction of a new anti-cancer treatment, death, loss to follow-up, withdrawal of consent, or end of the whole trial.
- p The patients will not be required to go to the clinic on Cycle 4 Days 2 and 15 and Cycle 8 Days 2 and 15.
- q Only patients completed the activity up to until the cut off date for the primary report. All remaining patients will undergo EOT and 30 days visits safety procedures only.

TABLE OF CONTENTS

TITLE PAGE	1

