6.2.3 Follow-up period and trial completion

6.2.3.1 End-of-treatment visit

The EOT visit will be performed after permanent discontinuation of trial medication for any reason, as soon as possible, but no later than 7 days after permanent discontinuation of the trial medication or when the Investigator decided with the patient to permanently discontinue the trial medication or became aware that the trial medication had been terminated.

The assessments of the EOT visit will then be performed instead of at the next planned visit. If the patient finishes active treatment without having PD, tumour assessment/imaging must be performed at the time of treatment discontinuation, unless it has been done within the past 4 weeks.

For patients still on treatment with ezabenlimab at the time point of this protocol amendment, the investigators are asked to prepare for discontinuation of patients from the current investigational treatment with ezabenlimab and to switch them to alternative available treatment options outside of the current protocol no later than by the final availability of ezabenlimab in August 2023 the latest. After this date treatment with the ezabenlimab will no longer be available.

For these patients only EOT visit will be performed. 30-day post-treatment safety visit as well as Progression-free survival visits are not applicable.

6.2.3.2 30-day post-treatment safety visit

The safety follow-up visit is performed 30 (+2) days after permanent discontinuation of the trial medication. The information collected at this visit must include all new AEs that occurred after the EOT visit, and a follow-up of AEs ongoing at EOT.

A patient will be considered as having completed the trial if he/she discontinues because of PD and has performed the safety follow-up visit 30 days after EOT, or was lost to follow up, or withdrew consent for further evaluation at the EOT visit. If the patient discontinues for any other reason, he/she will be considered as withdrawn.

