7.3.1 Primary endpoint analyses

In order to identify the MTD of the trial, the number of patients with DLTs at each dose level during the Phase Ia MTD evaluation period (first three weeks) must be presented. Patients who discontinue during the first treatment course for reasons other than a DLT will be excluded from the determination of the MTD.

In addition, the number of patients with DLTs that occurred during the entire treatment period, including Phase Ia and Phase Ib, will be summarised at each dose level. The BLRM will be rerun to re-evaluate the MTD and RP2D together with all relevant data collected during Phase Ib.

For the primary efficacy endpoint of Phase Ib, objective response rate (ORR) will be summarised and presented with 95% two-sided confidence intervals using the Clopper-Pearson method.

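### A stop decision at a scheduled visit replaces that visit's haematology and chemistry with an EOT visit that has neither, so a laboratory DLT may go undetected

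*Protocol*

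**What the plan says.** Three places substitute the EOT visit for another visit:

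- Flow Chart 1 (Phase Ia), footnote o: "the EOT visit assessments should be performed instead of the scheduled visit assessments".
- Flow Chart 2 (Phase Ib), footnote n: "the EOT visit assessments should be performed instead of the scheduled visit".
- Section 6.2.3.1: "The assessments of the EOT visit will then be performed instead of at the next planned visit".

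In Flow Chart 1 the row "Hematology and Clinical Chemistry Labs" is marked at screening, Day 1, Days 8 and 15 (Cycle 1 only), Day 1 of later cycles and the 30-day follow-up. Its EOT cell is blank. The row "DLT Assessment (report required at Phase Ia Cycle 1") is marked at EOT. In Flow Chart 2, as extracted, the laboratory row is also blank at EOT.

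Section 5.3.4 takes the timing of safety blood samples from the flow charts and adds none at EOT. Section 5.3.4.3 names EOT for urinalysis only.

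Section 7.3.1 states the consequence for Phase Ia: "Patients who discontinue during the first treatment course for reasons other than a DLT will be excluded from the determination of the MTD".

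**The concern.** The plan asks for a DLT judgement at EOT without scheduling the blood results on which part of that judgement rests. Section 4.1.5 includes criteria that a single sample can meet: Grade 4 thrombocytopenia, Grade 4 AST or ALT of any duration, and raised AST or ALT with raised bilirubin. The missing sample falls on patients who are stopping drug, and toxicity is one reason to stop.

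In Cycle 1, whether a DLT is found decides how the patient is handled. Under Section 4.1.7 a DLT makes the patient evaluable. Without one, a patient who discontinues is left out of the MTD determination (Section 7.3.1) and may be replaced (Section 3.3.4.1); SAP Sections 5.1 and 6.3 drop replaced patients from the MTD set. In Phase Ib the number of patients with DLTs over the whole treatment period is a primary endpoint, so the same gap touches its ascertainment.

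**Working it through.** **1. Which draw is lost, and when is the next one?** Inputs: first dose on Day 1; DLT window Days 1 to 21 (Section 4.1.5); lab days from Flow Chart 1; 30-day visit at 30 to 32 days. Section 6.1 counts those days from the last administration, Section 6.2.3.2 from permanent discontinuation. From the last dose: 1 + 30 = Day 31 to 1 + 32 = Day 33. From discontinuation: stop day + 30 to + 32.

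| Stop decided at | Last earlier lab | Lab replaced | 30-day lab, from last dose | 30-day lab, from stop |
|---|---|---|---|---|
| Cycle 1 Day 8 | Day 1* | Day 8 | Days 31–33 | Days 38–40 |
| Cycle 1 Day 15 | Day 8 | Day 15 | Days 31–33 | Days 45–47 |
| Cycle 2 Day 1 (Day 22, no dose given) | Day 15 | Day 22 | Days 31–33 | Days 52–54 |

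*Or a screening sample from the preceding 72 hours (footnote d).

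In the first two rows the replaced draw lies inside Days 1 to 21 and no later scheduled draw does. In the third row the replaced draw is already outside the window, so nothing is lost for the Cycle 1 DLT count.

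**2. Phase Ib.** SAP Section 5.1 counts DLTs to the last dose + 30 days. Suppose the patient stops on Day 1 of a cycle, undosed, 21 days after the last dose. The window then has 30 − 21 = 9 days left. If a 30-day lab exists, it falls at 30 to 32 days after the last dose (Section 6.1 counting) and is inside the window only if drawn on day 30. The preceding lab is 21 days old up to Cycle 9 and 3 × 21 = 63 days old at Cycles 12, 15 and so on. The 63-day spacing comes from the lab schedule itself; the EOT rule only removes the draw then due. Cycles 10, 11, 13, 14 and so on have no labs due, so nothing is lost there.

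**3. How reliable are the table cells?** In Flow Chart 1 the urinalysis row, marked at screening and EOT only, agrees with Section 5.3.4.3. The columns therefore align and the blank EOT lab cell is credible. In Flow Chart 2 the last lab mark falls under PFS/OS follow-up, which footnote o describes as telephone contact, and the 30-day cell is blank. That mark may be displaced and should be checked against the formatted protocol.

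**4. What one lost DLT does to the model.** The protocol's Table 10.5.1: 1 already shows it. With 0/3 at 80 mg, moving from 0/3 to 1/3 at 240 mg changes the next recommended dose from 800 mg (Scenario 2) to 320 mg (Scenario 3).

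I also ran the Section 7.1.1 model on a grid with the Section 7.1.1.1 prior and d* = 800 mg. It gives P(overdose) at 800 mg of 0.070 for the prior (printed 0.070), 0.047 in Scenario 1 (printed 0.047) and 0.032 in Scenario 2 (printed 0.034). It does not reproduce Scenario 3: 0.121 at 240 mg and 0.188 at 320 mg, against 0.186 and 0.247 printed.

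| Data | Dose | P(overdose) if DLT found (1/3) | If lost and patient replaced (0/3) |
|---|---|---|---|
| First cohort, 80 mg | 240 mg | 0.450 | 0.007 |
| 0/3 at 80 mg, then 240 mg cohort | 400 mg | 0.250 | 0.005 |
| 0/3 at 80 mg, then 240 mg cohort | 480 mg | 0.303 | 0.008 |

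The EWOC limit is 0.25. The 240 mg case crosses it clearly. In the second cohort, 400 mg, the next level in Table 4.1.3: 1, sits at the limit; 480 mg is clearly above it but is not one of the example escalation levels.

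**The case against.** A reader might infer that laboratory DLTs go uncounted, or that the plan biases the DLT rate downward by a known amount. The documents do not support either reading. DLTs are recorded throughout the trial (Section 4.1.5). Clinically relevant laboratory changes are recorded as AEs (Section 5.3.6.8.1). Investigators must watch liver biochemistry at any point (Section 5.3.6.5.4), and Section 7.5 promises particular effort on potential DLTs. The SAP takes in unscheduled labs (Section 6.7) and labs up to 30 days after the last dose (Section 7.8.2.1). A DLT that is found would be counted.

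The Phase Ia route is also narrow. Discontinuation must be decided at Cycle 1 Day 8 or 15, when no dose is due, before blood is drawn, in a patient whose only DLT is a laboratory one and for whom no test is clinically prompted. A persisting treatment-related toxicity of Grade 2 or more that prevents Cycle 2 Day 1 dosing is itself a DLT. Grade 4 neutropenia must last more than 7 days, which one sample cannot show. The SRC reviews all Grade 2 or higher Cycle 1 toxicity, not only the DLT count.

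All of this stands and limits the point to possible non-detection. It does not close the gap: these routes rely on discretion or on symptoms, and none requires a blood sample inside the 21-day window once the scheduled one has been replaced.

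**Conclusion.** The gap is real in Flow Chart 1 and probable in Flow Chart 2, subject to checking that table. Following the plan as written, a patient who stops at a visit with labs due has no protocol-required haematology or chemistry that day. A laboratory DLT may then be missed and, in Cycle 1, the patient may be handled as a non-DLT discontinuation and left out of the MTD determination.

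The frequency cannot be estimated: the documents give neither the number of discontinuations at lab visits nor the rate of laboratory-only DLTs. The model figures show what one lost DLT would do in a three-patient cohort, assuming the patient is replaced by one without a DLT. They say nothing about how likely that is.

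A related inconsistency concerns patients still on drug at the last amendment. Section 6.2.3.1 gives them an EOT visit only, with the 30-day visit not applicable; Flow Chart 2 footnote q gives remaining patients both visits. Under the first reading they have no scheduled blood safety labs at or after EOT.

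**What to change.** Amend footnote o (Flow Chart 1), footnote n (Flow Chart 2) and Section 6.2.3.1 so that haematology and chemistry due at the replaced visit are still drawn. Marking the laboratory row at EOT in both charts would do the same job. Check and correct the 30-day laboratory cell in Flow Chart 2. Reconcile Section 6.2.3.1 with footnote q on which visits apply to patients on drug at the last amendment.

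The cost is one routine local blood sample that was already due, plus a flow-chart and footnote edit. No SAP change is needed, because Section 7.8.2.1 already treats labs up to 30 days after the last dose as on-treatment.
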